**Table 9: Schedule of Events and Study Procedures, Study Group C.**

Study day		1	2	4	8	29	32	36	57	180	183	187	208	304	545
Days after most recent vaccination		0	1	3	7	28	3	7	28	151	3	7	28	124	365
Visit Window ( $\pm$ number of days)		0	0	1	1	3	1	1	3	7	1	1	3	14	14
Study visit		01	02P	03	04	05	06	07	08	09	10	11	12	13	14P
Clinical Evaluations and Procedures	Tube														
Assessment of eligibility		X													
Assessment of individual halting criteria						X				X					
Review medical history and con meds 		X	X	X	X	X	X	X	X	X	X	X	X	X	X
Vital signs (blood pressure, pulse, and oral temperature  )		X		X	X	X	X	X	X	X	X	X	X 	X 	
Enrollment		X													
Study Product Injection		I-1				I-2				I-3					
Targeted physical exam		{X}		{X}	{X}	{X}	{X}	{X}	{X}	{X}	{X}	{X}	{X}	{X}	
Pre-administration reactogenicity assessment		X				X				X					
Evaluate study product injection site		X		X	X	X	X	X		X	X	X			
Provide and explain use of memory aid and thermometer		X				X				X					
Review memory aid			X	X	X		X	X			X	X			
Collection of solicited AEs		X	X	X	X	X	X	X		X	X	X			

Study day		1	2	4	8	29	32	36	57	180	183	187	208	304	545
Days after most recent vaccination		0	1	3	7	28	3	7	28	151	3	7	28	124	365
Visit Window ( $\pm$ number of days)		0	0	1	1	3	1	1	3	7	1	1	3	14	14
Study visit		01	02P	03	04	05	06	07	08	09	10	11	12	13	14P
Clinical Evaluations and Procedures	Tube														
Collection of unsolicited AEs and SAEs 		X	X	X	X	X	X	X	X 	X	X	X	X	X	X
Pregnancy test (urine) 		X				X				X					
WBC, hemoglobin, platelets (mL)	EDTA	3			3	3		3	3	3	3	3	3	3	
Creatinine, ALT 	SST	10			10	10		10	10	10		10	10		
Serum collection for antibody assays and secondary research (mL)	SST	8.5			8.5	8.5		8.5	8.5	8.5		8.5	8.5	8.5	
PBMC isolation for secondary research (mL)	NaHep/ACD 	60			60	60		60	60	60		60	34	60	
Whole blood collection for gene expression assays	PAXGene	2.5			2.5	2.5		2.5		2.5		2.5			
Total volume per visit (mL)		84			84	84		84	84	84		84	55.5	68.5	
Cumulative volume (prior 56 days)		113.5			197.5	281.5		365.5	420	84		168	223.5	68.5	

{ } required at this visit only if clinically indicated

P=phone assessment

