3.2. Study Endpoints or Outcome Measures

3.2.1. Primary

- Occurrence of study vaccine-related SAEs from the time of the first study vaccination through approximately 12 months after the last study vaccination
- Occurrence of solicited injection site and systemic reactogenicity events from the time of each study vaccination through 7 days after each study vaccination
- Occurrence of clinical safety laboratory AEs from the time of each study vaccination through approximately 28 days after each study vaccination
- Occurrence of all unsolicited AEs, regardless of the assessment of seriousness or relatedness, from the time of each study vaccination through 28 days after each study vaccination
- Occurrence of SAEs, MAAEs, NOCMCs, and PIMMCs from the time of the first study vaccination through approximately 12 months after the last study vaccination

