3.3. Study Definitions and Derived Variables

Seroconversion is defined as a fourfold rise from baseline.

Clinical laboratory evaluations, vital signs, reactogenicity, and immunogenicity will be assessed on the day of, prior to the first study product injection (Day 1) to establish baseline. If a single ELISA result is below the lower limit of quantification (LLOQ) or above the upper limit of quantification (ULOQ) then the result will be imputed as LLOQ or ULOQ, respectively. If both ELISA results are below LLOQ, then the value will be imputed as $\frac{1}{2} \times \text{LLOQ}$. If both ELISA results are above ULOQ, then ULOQ will be reported.

Any medical condition that is present at the time that the subject is screened will be considered baseline and not reported as an AE. However, if the existing severity of any pre-existing medical condition increases, it will be recorded as an AE.

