4. INVESTIGATIONAL PLAN

4.1. Overall Study Design and Plan

This is a Phase 1, open label, dose-escalation clinical trial to evaluate the safety, reactogenicity, and immunogenicity of Sm-p80 + GLA-SE candidate schistosomiasis vaccine (SchistoShield®) in healthy adults 18 through 55 years of age. The Sm-p80 antigen is a recombinant protein produced in *E. coli* and GLA-SE is an immunological adjuvant.

Five treatment groups, each including nine subjects, will receive three intramuscular (IM) injections of 0.5 mL of designated study product on either Days 1, 29, and 57 or on Days 1, 29, and 180. Group A (unadjuvanted comparator) will receive 100 µg Sm-p80 alone on Days 1, 29, and 57; Group B (low dose standard schedule) will receive 10 µg Sm-p80 + 5 µg GLA-SE on Days 1, 29, and 57; Group C (mid dose delayed booster) will receive 30 µg Sm-p80 + 5 µg GLA-SE on Days 1, 29, and 180; Group D (mid dose standard schedule) will receive 30 µg Sm-p80 + 5 µg GLA-SE on Days 1, 29, and 57; Group E (high dose standard schedule) will receive 100 µg Sm-p80 + 5 µg GLA-SE on Days 1, 29, and 57. Dose escalation will proceed as described in the Protocol Summary (protocol v2.0).

Reactogenicity will be measured by the occurrence of solicited injection site and systemic reactions from the time of each study product injection through seven days after each study product injection. Unsolicited AEs of all severities, and concomitant medications, will be collected from the time of each study product injection through the next 28 days. During period of follow-up outside of the 28-day post-vaccination interval, only SAEs, medically attended adverse events (MAAEs), new onset chronic medical conditions (NOCMCs), and potentially immune-mediated medical conditions (PIMMCs) will be collected. Clinical laboratory evaluations for safety will be performed on venous blood collected prior to, and approximately seven days after, each study vaccination.

Immunogenicity testing will include measuring titers of total IgG against the Sm-p80 protein by ELISA. Gene expression will be evaluated using RNA Seq analysis from whole blood.

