14.1 Description of Study Subjects

14.1.1 Disposition of Subjects

Table 8: Subject Disposition by Treatment Group

[Implementation Note: Percentages are calculated using the denominators displayed in the header. Listings should be referenced by title for clarity.]

Subject Disposition	Group A: 100 µg Sm-p80 (unadjuvanted) (N=X)		Group B: 10 µg Sm-p80 + 5 µg GLA-SE (N=X)		Group C: 30 µg Sm-p80 + 5 µg GLA-SE (delayed booster) (N=X)		Group D: 30 µg Sm-p80 + 5 µg GLA-SE (N=X)		Group E: 10 µg Sm-p80 + 5 µg GLA-SE (N=X)		All Subjects (N=X)	
	n	%	n	%	n	%	n	%	n	%	n	%
Screened	--	--	--	--	--	--	--	--	--	--	x	--
Enrolled/Randomized	x	100	x	100	x	100	x	100	x	100	x	100
Received One Scheduled Treatment	x	xx	x	xx	x	xx	x	xx	x	xx	x	xx
Received Two Scheduled Treatments	x	xx	x	xx	x	xx	x	xx	x	xx	x	xx
Received All Scheduled Treatments ^a	x	xx	x	xx	x	xx	x	xx	x	xx	x	xx
Completed All Safety Blood Draws Groups A, B, D, E [Days 1, 8, 29, 36, 57, 64, 85] Group C [Days 1, 8, 29, 36, 57, 180, 187, 208]												
Completed All Immunogenicity Blood Draws for Antibody Assays Groups A, B, D, E [Days 1, 8, 29, 36, 57, 64, 85, 181] Group C [Days 1, 8, 29, 36, 57, 180, 187, 208, 304]												
Completed Follow-up ^a Groups A, B, D, E (Study Day 422) Group C (Study Day 545)												
Completed Per Protocol ^b												

Note: N = Number of subjects enrolled to the specified treatment group.

^a Refer to Listing 16.2.1 for reasons subjects discontinued or terminated early.

^b Refer to Listing 16.2.3 for reasons subjects are excluded from the Analysis populations .

Table 9: Analysis Populations by Treatment Group

Analysis Populations	Reason Subjects Excluded	Group A: 100 µg Sm-p80 (unadjuvanted) (N=X)		Group B: 10 µg Sm-p80 + 5 µg GLA-SE (N=X)		Group C: 30 µg Sm-p80 + 5 µg GLA-SE (delayed booster) (N=X)		Group D: 30 µg Sm-p80 + 5 µg GLA-SE (N=X)		Group E: 100 µg Sm-p80 + 5 µg GLA-SE (N=X)		All Subjects (N=X)	
		n	%	n	%	n	%	n	%	n	%	%	n
Safety Population	Any Reason	x	xx	x	xx	x	xx	x	xx	x	xx	x	xx
	Did not receive study product												
	[Reason 2]												
mITT Immunogenicity Population	Any Reason												
	Did not have post-baseline immunogenicity assay												
	[Reason 2]												
Per Protocol Population	Any Reason												
	Did not have post-baseline immunogenicity assay												
	Found to be ineligible at baseline after the enrollment												
	[Reason 3]												

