	Median			N/A		
	(Minimum, Maximum)			N/A		
Study Day 180 (Group C: Pre-Dose 3)	n	N/A	N/A		N/A	N/A
	GMT (95% CI)	N/A	N/A		N/A	N/A
	Mean	N/A	N/A		N/A	N/A
	Std. Dev.	N/A	N/A		N/A	N/A
	Median	N/A	N/A		N/A	N/A
	(Minimum, Maximum)	N/A	N/A		N/A	N/A

Table 15: Anti-Sm-p80 ELISA Total IgG Geometric Mean Titers (GMT) Results with 95% Confidence Intervals by Time Point and Treatment Group, mITT Immunogenicity Population (Continued)

Time Point	Statistic	Group A: 100 µg Sm-p80 (unadjuvanted) (N=X)	Group B: 10 µg Sm-p80 + 5 µg GLA-SE (N=X)	Group C: 30 µg Sm-p80 + 5 µg GLA-SE (delayed booster) (N=X)	Group D: 30 µg Sm-p80 + 5 µg GLA- SE (N=X)	Group E: 100 µg Sm-p80 + 5 µg GLA-SE (N=X)
Study Day 187 (Group C: 7 Days Post Dose 3)	n	N/A	N/A		N/A	N/A
	GMT (95% CI)	N/A	N/A		N/A	N/A
	Mean	N/A	N/A		N/A	N/A
	Std. Dev.	N/A	N/A		N/A	N/A
	Median	N/A	N/A		N/A	N/A
	(Minimum, Maximum)	N/A	N/A		N/A	N/A
Study Day 181 (Groups A, B, D, E: 124 Days Post Dose 3)	n			N/A		
	GMT (95% CI)			N/A		
	Mean			N/A		
	Std. Dev.			N/A		
	Median			N/A		
	(Minimum, Maximum)			N/A		
Study Day 208 (Group C: 28 Days Post Dose 3)	n	N/A	N/A		N/A	N/A
	GMT (95% CI)	N/A	N/A		N/A	N/A
	Mean	N/A	N/A		N/A	N/A

Table 15: Anti-Sm-p80 ELISA Total IgG Geometric Mean Titers (GMT) Results with 95% Confidence Intervals by Time Point and Treatment Group, mITT Immunogenicity Population (Continued)

Time Point	Statistic	Group A: 100 µg Sm-p80 (unadjuvanted) (N=X)	Group B: 10 µg Sm-p80 + 5 µg GLA-SE (N=X)	Group C: 30 µg Sm-p80 + 5 µg GLA-SE (delayed booster) (N=X)	Group D: 30 µg Sm-p80 + 5 µg GLA- SE (N=X)	Group E: 100 µg Sm-p80 + 5 µg GLA-SE (N=X)
	Std. Dev.	N/A	N/A		N/A	N/A
	Median	N/A	N/A		N/A	N/A
	(Minimum, Maximum)	N/A	N/A		N/A	N/A
Study Day 304 (Group C: 124 Days Post Dose 3)	n	N/A	N/A		N/A	N/A
	GMT (95% CI)	N/A	N/A		N/A	N/A
	Mean	N/A	N/A		N/A	N/A
	Std. Dev.	N/A	N/A		N/A	N/A
	Median	N/A	N/A		N/A	N/A
	(Minimum, Maximum)	N/A	N/A		N/A	N/A

Note: N = Number of subjects in the mITT Immunogenicity Population; n = Number of subjects with results at the given time point. GMT = Geometric mean titer.

Pseudo Code:

```
/*Geometric Mean Titers*/
data dsn2;
  set dsn1;
  log_aval = log(aval);
proc means data=dsn2 n mean clm noint;
  by stdy trta;
  var log_aval;
  output out= gmt0(drop=_type_ _freq_)
    n= n
    mean= mean
    std= sd
    median= med
    max= max
    min= min
    lclm=lclm
    uclm=uclm;
data gmt;
  set gmt0;
  gmt = put(exp(mean),8.1); /*geometric mean titer*/
  gmt_l = put(exp(lclm), 8.1); /*lower bound*/

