Time Point	Treatment Group	N	None		Mild / Grade 1		Moderate/ Grade 2		Severe/ Grade 3		Missing	
			n	%	n	%	n	%	n	%	n	%
Study Day 208	30 µg Sm-p80 + 5 µg GLA-SE (delayed booster)											
Max Severity Post Baseline	100 µg Sm-p80 (unadjuvanted)											
	10 µg Sm-p80 + 5 µg GLA-SE											
	30 µg Sm-p80 + 5 µg GLA-SE (delayed booster)											
	30 µg Sm-p80 + 5 µg GLA-SE											
	100 µg Sm-p80 + 5 µg GLA-SE											

Note: The “Max Post Baseline” rows indicate the maximum severity experienced by each subject at any time point post baseline, including unscheduled assessments.

Note: N = Number of subjects in the Safety Population with lab results at the specified visit.

Tables with similar format to [Table 59](#):**Table 60: Laboratory Results by Parameter, Maximum Severity, Time Point, and Treatment Group – Creatinine****Table 61: Laboratory Results by Parameter, Maximum Severity, Time Point, and Treatment Group -- Alanine Aminotransferase**

Table 62: Abnormal Laboratory Results Related to Study Treatment by Parameter, Maximum Severity, Time Point, and Treatment Group – Any Chemistry Parameter

[Implementation Note: Only scheduled time points at which at least one related abnormal lab result is observed in any treatment group will be shown. Add group name to treatment, e.g. "Group A: 100 µg Sm-p80 (unadjuvanted)".]

Time Point	Treatment Group	N	None			Mild / Grade 1		Moderate/ Grade 2		Severe/ Grade 3	
			n	%	n	%	n	%	n	%	n
Study Day 1 (Baseline)	100 µg Sm-p80 (unadjuvanted)	x	x	x	x	x	x	x	x	x	x
	10 µg Sm-p80 + 5 µg GLA-SE										
	30 µg Sm-p80 + 5 µg GLA-SE (delayed booster)										
	30 µg Sm-p80 + 5 µg GLA-SE										
	100 µg Sm-p80 + 5 µg GLA-SE										
Study Day 8	100 µg Sm-p80 (unadjuvanted)										
	10 µg Sm-p80 + 5 µg GLA-SE										
	30 µg Sm-p80 + 5 µg GLA-SE (delayed booster)										
	30 µg Sm-p80 + 5 µg GLA-SE										
	100 µg Sm-p80 + 5 µg GLA-SE										
Study Day 29	100 µg Sm-p80 (unadjuvanted)										
	10 µg Sm-p80 + 5 µg GLA-SE										
	30 µg Sm-p80 + 5 µg GLA-SE (delayed booster)										
	30 µg Sm-p80 + 5 µg GLA-SE										
	100 µg Sm-p80 + 5 µg GLA-SE										
Study Day 36	100 µg Sm-p80 (unadjuvanted)										
	10 µg Sm-p80 + 5 µg GLA-SE										
	30 µg Sm-p80 + 5 µg GLA-SE (delayed booster)										
	30 µg Sm-p80 + 5 µg GLA-SE										
	100 µg Sm-p80 + 5 µg GLA-SE										

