Table 62: Abnormal Laboratory Results Related to Study Treatment by Parameter, Maximum Severity, Time Point, and Treatment Group – Any Chemistry Parameter (Continued)

Time Point	Treatment Group	N	None		Mild / Grade 1		Moderate/ Grade 2		Severe/ Grade 3	
			n	%	n	%	n	%	n	%
Study Day 57	100 µg Sm-p80 (unadjuvanted)									
	10 µg Sm-p80 + 5 µg GLA-SE									
	30 µg Sm-p80 + 5 µg GLA-SE (delayed booster)									
	30 µg Sm-p80 + 5 µg GLA-SE									
	100 µg Sm-p80 + 5 µg GLA-SE									
Study Day 64	100 µg Sm-p80 (unadjuvanted)									
	10 µg Sm-p80 + 5 µg GLA-SE									
	30 µg Sm-p80 + 5 µg GLA-SE									
	100 µg Sm-p80 + 5 µg GLA-SE									
Study Day 85	100 µg Sm-p80 (unadjuvanted)									
	10 µg Sm-p80 + 5 µg GLA-SE									
	30 µg Sm-p80 + 5 µg GLA-SE									
	100 µg Sm-p80 + 5 µg GLA-SE									
Study Day 180	30 µg Sm-p80 + 5 µg GLA-SE (delayed booster)									
Study Day 187	30 µg Sm-p80 + 5 µg GLA-SE (delayed booster)									
Study Day 208	30 µg Sm-p80 + 5 µg GLA-SE (delayed booster)									
Max Severity Post Baseline	100 µg Sm-p80 (unadjuvanted)									
	10 µg Sm-p80 + 5 µg GLA-SE									
	30 µg Sm-p80 + 5 µg GLA-SE (delayed booster)									
	30 µg Sm-p80 + 5 µg GLA-SE									
	100 µg Sm-p80 + 5 µg GLA-SE									

Table 62: Abnormal Laboratory Results Related to Study Treatment by Parameter, Maximum Severity, Time Point, and Treatment Group – Any Chemistry Parameter (Continued)

Time Point	Treatment Group	N	None			Mild / Grade 1		Moderate/ Grade 2		Severe/ Grade 3			
			n	%	n	%	n	%	n	%	n		
Note: The “Max Post Baseline” rows indicate the maximum severity experienced by each subject at any time point post baseline.													
Note: N = Number of subjects in the Safety Population with lab results at the specified visit.													

Tables with similar format to [Table 62](#):

Table 63: Abnormal Laboratory Results Related to Study Treatment by Parameter, Maximum Severity, Time Point, and Treatment Group – Creatinine

Table 64: Abnormal Laboratory Results Related to Study Treatment by Parameter, Maximum Severity, Time Point, and Treatment Group – Alanine Aminotransferase

Table 65: Laboratory Summary Statistics by Parameter, Time Point, and Treatment Group – Creatinine (mg/dL)

[Implementation Note: Add group name to treatment, e.g. "Group A: 100 µg Sm-p80 (unadjuvanted)."]

Time Point	Treatment Group	N	Mean	Standard Deviation	Median	Min, Max
Study Day 1 (Baseline)	100 µg Sm-p80 (unadjuvanted)	x	xx.x	xx.x	xx.x	xx, xx

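### The laboratory Max Severity Post Baseline rows are not limited to the 28-day endpoint window, so Group C's Day 180 pre-dose-3 draw enters its per-subject maximum and can inflate it relative to the endpoint.

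*SAP*

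**What the plan says.** **Endpoint.** SAP 3.2.1 (and Protocol 3.3.1) lists as primary: "Occurrence of clinical safety laboratory AEs from the time of each study vaccination through approximately 28 days after each study vaccination".

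**Summary row.** The mock-ups for Tables 59-64 and 67-74 end with a Max Severity Post Baseline row for each group. The note under Tables 59, 67 and 71 says that these "rows indicate the maximum severity experienced by each subject at any time point post baseline, including unscheduled assessments". The note under Table 62 says only that they "rows indicate the maximum severity experienced by each subject at any time point post baseline", with no mention of unscheduled tests. Neither version sets a time limit after a dose.

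**Baseline.** SAP 3.3 assesses laboratory values "prior to the first study product injection (Day 1) to establish baseline". Everything later is post baseline.

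**Schedule.** SAP 4.1 states that "Group C (mid dose delayed booster) will receive 30 µg Sm-p80 + 5 µg GLA-SE on Days 1, 29, and 180". SAP Table 8 lists the safety draws for "Group C [Days 1, 8, 29, 36, 57, 180, 187, 208", and for Groups A, B, D and E on Days 1, 8, 29, 36, 57, 64 and 85. Table 15 labels the Group C visit "Study Day 180 (Group C: Pre-Dose 3".

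**Collection text.** SAP 4.5.1 gives the times for laboratory AEs as the injection day before the injection, and about 7 and about 28 days after it.

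**The concern.** The endpoint and the row that comes closest to summarising it cover different periods. Between Group C's Day 57 visit and dose 3, footnote 3 of Protocol Table 9 restricts event collection to SAEs, MAAEs, NOCMCs and PIMMCs. A graded value found just before dose 3 falls in that interval, yet it enters the same maximum as values taken 7 or 28 days after a dose.

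This matters because the overall AE summary, Table 18, has no row of its own for laboratory AEs. The Max rows are the only across-visit, per-subject summaries of laboratory severity. SAP 6.2 puts Tables 59-61 and 67-70 in the interim reports, and SAP 6.6.2 allows interim results to be published or used by the product developers. The second interim waits at least for Group C's Day 208, so it would carry the Day 180 values. With nine subjects, one reclassified subject moves a group's percentage by 1/9, or 11 points.

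**Working it through.** **1. The plan's own interval.** SAP Table 3 gives 151 days since the most recent vaccination at Day 180. Check: 180 - 29 = 151. The ±7-day visit window gives 144 to 158 days if dose 2 was on Day 29.

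**2. Each scheduled post-baseline safety draw against the window.** Draws on injection days precede the injection, so the interval runs from the previous dose. The window is 28 days plus the 3-day visit allowance, 31 days.

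| Groups | Draw day (days since previous dose) | Outside window |
|---|---|---|
| A, B, D, E | 8 (7), 29 (28), 36 (7), 57 (28), 64 (7), 85 (28) | none of 6 |
| C | 8 (7), 29 (28), 36 (7), 57 (28), 180 (151), 187 (7), 208 (28) | 1 of 7: Day 180 |

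Windowed follow-up is equal across groups: 85 - 1 = 84 days in A, B, D and E, and (57 - 1) + (208 - 180) = 84 days in C. Limiting the maximum to the window gives six scheduled draws everywhere.

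**3. Unscheduled tests.** Protocol 7.2.1 allows repeats at any time in the study. The out-of-window time in which a repeat could count is 422 - 85 = 337 days in A, B, D and E, and (180 - 57) + (545 - 208) = 123 + 337 = 460 days in C.

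**4. Size of the scheduled-draw effect.** SAP Table 4 uses 1 - (1 - p)^n; with p = 0.20 and n = 9 this gives 0.866, as stated there. The same form is applied here across draws within a subject. Let q be the chance of a graded value at one draw. The documents do not give q, so a range is shown, with draws assumed independent and q constant.

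- Six draws: 1 - (1 - q)^6. Seven draws: 1 - (1 - q)^7. Difference: q(1 - q)^6.

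| q | 6 draws | 7 draws | Excess (points) | Expected extra subjects of 9 |
|---|---|---|---|---|
| 0.01 | 5.9% | 6.8% | 0.9 | 0.09 |
| 0.02 | 11.4% | 13.2% | 1.8 | 0.16 |
| 0.05 | 26.5% | 30.2% | 3.7 | 0.33 |
| 0.10 | 46.9% | 52.2% | 5.3 | 0.48 |
| 1/7 | 60.3% | 66.0% | 5.7 | 0.51 |
| 0.20 | 73.8% | 79.0% | 5.2 | 0.47 |

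The difference is largest at q = 1/7, where (1/7)(6/7)^6 = 0.0567. Positive correlation within a subject would generally lower these figures, because a subject with a graded Day 180 value would more often have an in-window grade already.

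**The case against.** The strongest reply is that the row claims no more than it delivers. SAP 9.6 introduces these tables as distributions of laboratory results and never names the Max row as the estimate of the primary endpoint. The row is openly labelled as any time after baseline. Day 180 has its own row, and Tables 57-58 list each abnormal result with planned time point and actual study day, so a reader can trace the value. In Tables 62-64 and 71-74 a Day 180 result counts only if judged related. Much of this stands. The label is honest and the information is recoverable by hand, but the per-time-point row alone does not let a reader take Day 180 out of a per-subject maximum.

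A second reply is that SAP 4.5.1 includes pre-injection draws among the laboratory-AE times and Protocol 8.5 grades every specimen after the first injection, so Day 180 may belong. This also has force: the documents disagree among themselves. But the 4.5.1 list equally takes in the Day 1 pre-dose draw, which is baseline. In Groups A, B, D and E the later pre-dose draws are also 28-day follow-up draws. Only Group C's Day 180 exposes the conflict, and it has to be settled in the text.

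Third, unscheduled out-of-window tests count in every group where the note admits them. That is correct: the Group C asymmetry concerns scheduled draws only.

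**Conclusion.** The point holds as a mismatch between the endpoint window, the collection text and the Max-row notes. Group C's maximum rests on seven scheduled draws against six, and it can be inflated relative to the endpoint. It changes only if a subject's Day 180 grade exceeds that subject's worst in-window grade. The excess is about 4 to 5 points at an assumed 5-10% per draw, and at most 5.7 points (about half a subject of nine) under independence and a constant rate.

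Three stronger readings are tempting, and the documents do not support them:

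- *That the primary endpoint is inflated in Group C.* The SAP does not designate this row as the endpoint analysis, and whether any grade changes depends on the data.
- *That a Group C versus Group D laboratory comparison is biased.* No laboratory difference, interval or test is planned; the analysis is descriptive.
- *That Group C has still more extra draws.* Protocol Table 9, as read, shows hematology marks on Days 183 and 304. Its own totals disagree: Day 183 has no volume, and Day 304 is 8.5 + 60 = 68.5 mL with no hematology tube. SAP Table 3 does not show the marks either. They may come from the PDF reading, and Day 183 would be in the window anyway. No magnitude should rest on them.

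**What to change.** 1. In Tables 59-64 and 67-74, define the Max row as the worst grade among results taken after a dose and through that dose's 28-day visit, including the visit window (up to 31 days).
2. Keep the Group C Day 180 row and label it a pre-dose-3 reference, outside the Max row.
3. Show out-of-window grades and unscheduled results in a separate row or listing, so that no safety data are lost.
4. Use one rule for unscheduled tests in the notes to Tables 59, 62, 67 and 71.
5. Reword SAP 4.5.1 so that it separates sampling times from the period in which a graded value counts toward the endpoint, and agrees with SAP 3.2.1.

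Make no change to the vital-sign tables (78-82) on this basis. Footnote 1 to the schedules has vital signs taken in the observation period after each injection, so removing Day 180 there would discard post-dose-3 readings.

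The cost is SAP wording and one derivation flag based on the dose dates and the actual study day of each result. Nothing extra is collected. It is best done before the second interim report.
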